Cover Page

Record (NCT) Identifier Number: NCT03658538

Johns Hopkins University
Unique Protocol ID: IRB00185955

Study Title: Motivational Interviewing and Air Cleaners for Smokers With COPD (MOVE COPD)

Principal Investigator: [name]

Protocol Date: February 4, 2022

MOVE COPD Study Protocol

Objectives

Specific Aim #1: To determine whether a multi-component environmental intervention to improve home air quality (PM, SHS and NO₂ reduction) will improve respiratory morbidity (i.e., symptoms, quality of life, lung function and reduce risk of exacerbations) in smokers with COPD.

Specific Aim #2: To determine whether a multi-component environmental intervention to improve home air quality (PM, SHS and NO₂ reduction) will be associated with intermediate outcome measures known to be linked with long term outcomes in COPD, including airway (induced sputum) and systemic (serum and urine) markers of inflammation and oxidative stress, in smokers with COPD.

Study Procedures

1. Study design, including the sequence and timing of study procedures.

We will recruit current smokers (n=150) with moderate to severe COPD and those still smoking after a one-month smoking cessation run-in period will be randomized (estimated 80% of original sample, goal n=120) to receive either 1) air cleaner (with HEPA filters for reduction of PM) and MI for SHS reduction or 2) sham air cleaners. All eligible participants will be offered smoking cessation counseling throughout the study period and will have air monitoring and outcomes assessed at randomization, and 3 and 6-months post intervention. All patients enrolled in this study will continue to have their usual care for COPD as determined by their primary care provider or their usual COPD caregiver. No treatments will be discontinued.

2. Screening Assessment Visit

The initial clinic visit will take place at the Johns Hopkins Asthma and Allergy Center. During the initial clinic visit participant eligibility will be established and informed consent obtained. The screening assessment visit is expected to take approximately 2 hours.

The screening assessment visit will include the following:

- Informed consent
- Pre- and Post-BD spirometry
- Eligibility assessment questionnaires
- Clinical Examination to include anthropometry, vitals and skinfold assessment

3. Home Air Quality Screening Assessment (IF APPLICABLE)

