Over the course of the enrollment period, we will assess each subject for 3 seven-day periods (at randomization, 3 months and 6 months post-intervention) to assure that each subject is examined in different seasons; and to evaluate the immediate as well as longer term effects of the interventions on air quality and COPD health. This approach is based on the measurement approach that we have previously demonstrated for PM reduction trials. Indoor air quality monitoring will be conducted over a 7-day period in the room where the participant is expected to spend the most time over the monitoring period.

During each home visit:

- 1) Monitors for air samples will be set up in the bedroom and in the room in which the participant spends most of his/her time.
- 2) Detailed questionnaire about home characteristics will be administered
- 3) A home inspection will be performed
- 4) Participants will be instructed on how to complete a Time Activity Diary (TAD) and symptom diary which is to be done during the time of the air monitoring period,
- 5) Outdoor air monitors will be placed in a convenient and secured location outside of each home
- 6) Dust collection in the main living area and bedroom at home.

The home visits will include the following:

- Environmental monitoring equipment set up and dust collection.
- Instructions on activity diary (TAD), symptom diary (BCSS)

Participant responsibilities:

- Activity diary (TAD daily)
- Breathlessness, Cough and Sputum Scale (BCSS daily)
- Dust collection

Household Inspection: At the time that monitoring is initiated, a trained home inspector will conduct a household inspection which will include the type, salient features and condition of the house including 1) type of home (detached, duplex, row house, apartment) and size of home; 2) type of

furnace (gas, oil, heat pump) as well as heating (radiator, forced air, electric space heater, other); 3) the presence of central or room air conditioning; dehumidifiers, or humidifiers, 4) evidence of cigarette smoke/smell of cigarettes/ashtrays. The home inspection will focus on the living/family room, the kitchen, basement, and the participant's bedroom and identify potential sources of PM, SHS and NO₂ as potential confounders to the effectiveness of home interventions.

Collect Dust samples: Study team member will vacuum settled dust samples from the room in which air pollution monitors have been placed to study allergens at home.

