- Breathing Tests: Spirometry will carry out to measure lung function. We will obtain at least three acceptable and reproducible spirometric maneuvers from a maximum of eight in accordance to the American Thoracic Society (ATS) and European Respiratory Society guidelines.
- Salivary cotinine will be assessed during each clinic visit to assess smoking status.
- Six Minute Walk Test will be assessed during each clinic visit to test participants exercise tolerance. Participant will be asked to walk for 6 minutes of a flat surface to see how far can go. If participants use oxygen when walking, they will use it for this test. As a safety precaution, the amount of oxygen in their blood will be measured using a pulse oximeter, which is a small device that attaches to the index finger.
- Blood Draw: Fasting blood sample will be collected to measure systemic markers of inflammation and oxidation, and it will include a complete blood count with differential (CBC with diff) to assess effects of pollution and air cleaners on inflammatory profile.

7. Telephone Calls

01 call (during the 1 month run-in period) for Motivational Interviewing for smoking cessation: All participants will receive 1 call for smoking cessation prior to randomization. *Additional counseling sessions will be scheduled for any participant or family member(s) interested in smoking cessation during this period.*

04 calls (between randomization and the 3 month-follow-up) for Motivational Interviewing for home/car smoking ban (HCSB): The MI-component of the intervention will be adapted from the PRIDE phone-based MI intervention and delivered by a health coach. Each participant will receive 4 phone sessions between baseline and the 3 month visit focused on implementing a home smoking ban. All participants regardless of randomization group will receive the 4 phone call sessions (between baseline and the 3 month clinic visit) focused on smoking cessation counseling. Only participants randomized to the active group will receive the additional Motivational Interviewing for HCSB during the calls.

04 Monthly calls (from randomization to 6 month-follow up) to assess Exacerbations and Health Care Utilization: Information on unscheduled doctor visits, emergency room visits, and days hospitalized, and intensive care unit admissions will be collected at each visit from all participants and by monthly telephone calls.

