03 Monthly Follow up calls (after final home visit) Individuals will also be contacted monthly for 3 months after the final home visit by study coordinators, in order to ascertain whether exacerbation events were experienced by participants. The Telephone Exacerbation questionnaire that will be administered, will take about 5 minutes.

8. Study duration and number of study visits required of research participants.

The study duration is 5 years and each subject will be enrolled for 9 months. There will be one screening assessment visit and one home air quality assessment visit (if applicable) prior to enrollment, 1 month of run-in period (including two MI sessions) and 3 home monitoring visits preceding 3 follow-up clinical visits.

9. Justification for inclusion of a placebo or non-treatment group.

Randomization: At the conclusion of the run-in period, subjects enrolled will be randomly assigned to one of two treatment arms: 1) active air cleaners and MI for SHS reduction (n=60) and 2) placement of sham air cleaners and continued smoking cessation counseling (n=60). Randomization will be stratified by season and will be performed by block to assure equal sized populations in each arm. This strategy also will ensure that each group is balanced with respect to season of randomization.

10. Treatment Groups.

- 1) **Active Treatment arm:** The active treatment arm will receive two active air cleaners with HEPA filters as well as 4 sessions of phone based motivational interviewing to support a home smoking ban and SHS reduction (in addition to the smoking cessation counseling received by all study participants).

Rationale: Two air cleaners will be deployed in the home to be consistent with our previous trials that have successfully reduced PM and improved respiratory morbidity. Air cleaners will have HEPA filters which remove PM. As portable air cleaners have not shown efficacy in reducing SHS exposure this intervention also targets a home smoking ban for both SHS and PM reduction, in order to provide greatest reduction in pollutant exposure and maximize ability to show that air quality improvement can improve health in smokers.

Active air cleaner: Air cleaners containing HEPA and capable of removing PM filter will be placed in the bedroom and room where the participant reports spending the most time. Air cleaners are

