Smoking Cessation counseling and Nicotine Replacement Therapy (NRT): Smoking Cessation counseling will be offered to all eligible participants throughout the study. Study will offer NRT to all participants during the Run-In period. If participants would like to continue NRT after the Run-In period they will be referred to the community resources provided during the Motivational Interviewing session.

Participants in the control group will receive 4 sessions of education smoking cessation counseling as an attention control condition. Cognitive based therapy will be provided to participants and will focus on anticipating triggers for relapse and developing coping strategies to deal with withdrawal. Problem solving and skills training will be integrated to support cessation. Participants will be paid \$25 for completing all four sessions to ensure completion. These incentives are provided regardless of behavior change and are included in this efficacy study to evaluate whether a full dose of intervention results in meaningful changes in behavior.

11. Definition of treatment failure or participant removal criteria.

Participants may be removed from the study early if they are not living in their home during the study time (including admission to the hospital). In these cases, monitoring of the home environment would not reflect exposure.

12. Description of what happens to participants receiving therapy when study ends or if a participant's participation in the study ends prematurely.

At the end of the study, participants in the control group will also receive active air cleaners.

13. Inclusion/Exclusion Criteria

Inclusion Criteria:

- 1) Age \geq 40 years,
- 2) Physician diagnosis of COPD,
- 3) GOLD Stage II-IV disease with (post-bronchodilator) FEV1/FVC $<$ 70% and FEV1 (% predicted) $<$ 80%. *IF FEV1/FVC < 70% and FEV1 (% predicted) \geq 80%, additional requirement will apply/will be asked: CAT score \geq 10 OR exacerbation history during the last 12 months. Also, IF available for screening purposes: participant can provide a previous PFT report within the last 6 months.*
- 4) Tobacco exposure \geq 10 pack-years, and

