## Analytical approach

We used descriptive statistics to characterize the patient sample, using proportions or means with standard deviations where appropriate. Descriptive statistics of central tendency and variability were generated. The distributions of each variable were assessed for normality, and appropriate transformations were made as necessary.

Primary analysis included an Intention-to-Treat analysis including all subjects randomized and having data at baseline and 6-month. The primary outcome measured included SGRQ score, and the secondary primary outcome, dyspnea, UCSD SOBQ. These outcomes were selected based on preliminary data showing an association with pollutant exposure and because they are measured with standardized instruments, which allowed for comparability across clinical trials. Furthermore, patient-reported outcomes provide insight into the practical effects of disease on everyday life and dyspnea is the primary reason for patients seeking medical care.

Secondary outcome measures included: CAT score, FEV1 and % change in FEV1 after albuterol. In addition, we evaluated respiratory exacerbations which were defined as a worsening of respiratory symptoms requiring antibiotics or oral corticosteroid use and acute health care utilization. The primary outcome for Specific Aim #2 is serum CRP concentrations, however several inflammatory and oxidative stress markers as outlined above will be measured.

In order to compare the change over time in our outcomes between treatment groups, analyses will consist of generalized linear mixed model (GLMM) to account for within-person correlations of the outcome. For the primary outcome measure we used a linear model:

$$E[Y_{ij}] = b_0 + b_1 \text{visit}_j + b_2 \text{treat}_i + b_3 \text{treat}_i * \text{visit}_j + a' \text{visit}_j * z_i$$

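### Protocol section 11 lets a hospital admission end a participant's whole study, for a reason that concerns only home air monitoring; outcome follow-up after removal is not provided for, so loss from the SGRQ analysis may depend on outcome and arm.

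*Protocol*

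**What the plan says.** **Removal rule.** Protocol section 11 states that participants "may be removed from the study early if they are not living in their home during the study time (including admission to the hospital"). The governing condition is not living at home, and hospital admission is named as an example of it. The reason follows at once: "In these cases, monitoring of the home environment would not reflect exposure". No length of stay, cause of admission, decision-maker or criterion for using the discretion is given.

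**What the reason concerns.** Protocol section 5 limits monitoring: "we will assess each subject for 3 seven-day periods (at randomization, 3 months and 6 months post-intervention". After the last of these there is no monitoring, only calls (section 7): "Individuals will also be contacted monthly for 3 months after the final home visit by study coordinators".

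**What happens after removal.** The heading of section 12 covers participation that ends early, but its whole text is: "At the end of the study, participants in the control group will also receive active air cleaners". A note at the end of section 5 allows questionnaires at home or by phone when a clinic visit cannot be attended. Section 7 says "days hospitalized, and intensive care unit admissions will be collected at each visit from all participants and by monthly telephone calls". Neither provision mentions removed participants.

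**Analysis.** The SAP (Analytical approach) defines the primary intention-to-treat analysis as "including all subjects randomized and having data at baseline and 6-month". Its Secondary outcome variables section counts hospitalization among the events that make an exacerbation severe. Specific Aim 1 names "lung function and reduce risk of exacerbations" among the expected benefits.

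**The concern.** The rule is wider than its reason. An invalid week of air data is a reason to discard or repeat that week. It does not explain ending SGRQ assessment, which does not depend on where the participant slept during monitoring.

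The trigger is also not neutral. A participant admitted to hospital is likely to be sicker than one who is not, and the trial hopes to change how often respiratory admissions occur. If admission leads to removal, and removal to exclusion from the 6-month comparison, the arms are compared after a selection that may differ between them. More removals in the control arm, among people who would have worsened more, would hide benefit. More removals in the active arm would exaggerate it.

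**Working it through.** The plan gives no removal rate, so it has no figure on this point to reproduce. The check has three parts.

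**1. From removal to loss from the primary analysis**
- Section 11: removal is from the study, not from air monitoring.
- Section 12, the section 5 note and section 7: none says that a removed participant is still assessed.
- SAP, Analytical approach: 6-month data are required for inclusion.
- Result: a participant removed before month 6, and not followed, is excluded from the SGRQ analysis even if a 3-month SGRQ exists.

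**2. How much of the time the stated reason reaches**
- Assumption: 3 months = 91 days, so monitoring weeks start on days 0, 91 and 182 and the last ends at day 189.
- Monitored share = 21/189 = 11.1%.
- For a stay of L days, with admission dates spread evenly over the 189 days (assumed), the start days whose stay touches a monitoring week number 7 + 2 × (7 + L − 1) = 21 + 2(L − 1).

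| Stay L (assumed) | Start days touching a week | Share |
|---|---|---|
| 3 days | 25 of 189 | 13.2% |
| 5 days | 29 of 189 | 15.3% |
| 10 days | 39 of 189 | 20.6% |

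So about 79% to 87% of admissions would leave every monitoring week intact.

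**3. Size of the bias**
- Let p be the share removed in an arm, and w how much worse (in SGRQ points) the removed would have changed than the retained.
- Mean change in all = (mean change in retained) + p × w. Hence retained mean = full mean − p × w.
- Bias in active minus control = p(control) × w(control) − p(active) × w(active). With a common w this is (p(control) − p(active)) × w. A positive value means toward no effect, since a lower SGRQ is better here.
- The SAP's minimal clinically important difference is 4. The rates and w below are assumptions.

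| Control vs active removal | w = 4 | w = 8 | w = 12 |
|---|---|---|---|
| 10% vs 5% (6 vs 3 of 60) | +0.20 | +0.40 | +0.60 |
| 5% vs 10% | −0.20 | −0.40 | −0.60 |
| 10% vs 10% | 0 | 0 | 0 |

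- Relative to 4 points: 0.20/4 = 5% and 0.60/4 = 15%.
- Each excess removal in an arm of 60 shifts the difference by w/60: 4/60 = 0.07 to 12/60 = 0.20.
- Milder case: the removed are stably worse and do not deteriorate. If they are 10 points worse at month 6 (assumed), the SAP's correlation of 0.86 gives w = 10 × (1 − 0.86) = 1.4, and the bias at 10% vs 5% is 0.05 × 1.4 = 0.07.
- Sampling error for scale: with the SAP's SD of 16.7 and correlation 0.86, the SD of change is 16.7 × √(2 × 0.14) = 8.84, and the standard error of the difference is 8.84 × √(2/60) = 1.61. So 0.2 to 0.6 points is about 0.12 to 0.37 standard errors.

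A mixed model on all available visits does not settle the matter. If the worsening starts with the event that triggers removal, earlier visits carry no information about it, and the model returns the same biased difference.

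**The case against.** The case for leaving the text alone is a fair one.

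- **The rule is permissive and about residence.** It says that participants may be removed, and admission is a parenthetical example of not living at home. The exclusions for living elsewhere and for planning to move show the same purpose. This stands: a reader might infer that every admission leads to removal, but the documents do not say so and show no practice. Discretion without criteria is not a safeguard, however. Blinding is described for participants, and nothing says that whoever decides on removal is unaware of the arm.
- **Collecting hospital days from all participants is compatible with a discretionary rule.** This also stands. A reader might infer an outright contradiction; strictly there is none. What is missing is a statement of how the two work together.
- **A route for follow-up exists.** Home or phone questionnaires and monthly calls could serve removed participants, and neither provision excludes them. That makes the repair easy, but neither is extended to them.
- **The exacerbation endpoint is largely protected.** A reader might infer that removal erases the exacerbation itself. It need not: a COPD admission that triggers removal is already an event in the yes/no analysis. The remaining risk is narrower: removed participants could be dropped from that model, or later exacerbations missed after a non-respiratory admission.
- **The SGRQ loss also depends on the SAP's 6-month data requirement,** which affects every dropout. True; section 11 is one route into that wider gap, but it is a route the protocol itself opens.
- **The size is assumed and small against sampling error.** Correct, and if the intervention works as hoped the likelier direction is toward no effect.

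**Conclusion.** The concern holds as a risk created by a stated rule, not as a demonstrated bias. Section 11 permits whole-study removal for a reason that reaches only the monitoring weeks. Nothing in the available text keeps outcome follow-up afterwards, and the SAP then excludes anyone without 6-month data. Because the trigger overlaps with an outcome that Aim 1 expects to improve, the loss may be related to outcome and arm.

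Size and direction are unknown. The 0.2 to 0.6 points rest wholly on assumed removal of 10% versus 5% and w of 4 to 12. The milder case gives 0.07, and equal removal with equal worsening gives zero. It would be wrong to conclude that the SGRQ result is biased, or in which direction. If few or no participants were removed, a table of removals closes the point. The change is worth making because it is cheap and removes an avoidable source of selection.

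**What to change.** **Protocol.** Reconcile section 11 with the hospital-use collection in section 7, the SAP's severe-exacerbation definition and the SAP's 6-month data requirement. State that absence from home or admission invalidates only the affected week's air data, which is marked missing or rescheduled. State that SGRQ and monthly-call follow-up continue for every randomized participant, using the home or phone option already in section 5. This concerns data collection only; treatment and care are unchanged. Cost: a short amendment and a few more phone questionnaires.

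**If follow-up is already complete,** as the SAP's largely past tense suggests:
1. Report removals by arm, reason and timing.
2. Keep all randomized participants in the exacerbation analysis, whether or not an event was recorded. Count events up to and including the admission, and account for shortened follow-up. Keeping only removed participants who had an event would select on the outcome.
3. If anyone was removed before month 6, add one SGRQ sensitivity analysis that assigns them a worse change, varied separately by arm (for example 0, 4, 8 and 12 points), so that both directions are shown.

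Cost: one table, a clear rule for the exacerbation model and, if needed, one sensitivity analysis.

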## MOVE COPD Study Statistical Analysis Plan

### Study Statistics

#### Primary outcome variable.

**Outcome for Specific Aim #1** was assessed at the end of each monitoring period (except exacerbations and health care utilization outcomes, which was assessed by monthly telephone calls).

**The primary outcome was health-related QOL determined using St. George's Respiratory Questionnaire (SGRQ).**

**Quality of Life:** Health-related QOL was determined using the St. George's Respiratory Questionnaire (SGRQ). The SGRQ is a disease specific instrument that contains 50 items in three subscales (symptoms, activity, and impact). Each response has an empirically derived weight, and the total score is calculated from responses to all 50 items.

